## 2.3.7.8.1 Secondary Endpoints

Secondary endpoints include:

- Clinically significant improvement in one or more radicular symptoms or myelopathy at each annual timepoint compared to baseline in the IDE study for the Simplify Disc and for the historical control ACDF. The data collected will reflect the number of patients who improved (numbers will be stratified to reflect clinical improvement), who remain unchanged, and who deteriorated at each study time point. These endpoints will be graded and defined as follows:
  - A visual analog scale (VAS) will be used to evaluate each of the following pain locations:
    - Neck and arm pain (to allow comparison to ACDF control)
    - Neck pain (Simplify Disc Only)
    - Left arm pain;(Simplify Disc Only)
    - Right arm pain;(Simplify Disc Only

Changes of at least 20 mm on a 100 mm scale will be regarded as clinically significant.

- Motor status A change of one or more grade levels in muscle strength will be regarded as clinically significant.
- Sensory status Sensation will be graded as normal or abnormal (diminished or absent). Any changes from abnormal to normal or absent to diminished will be regarded as clinically significant improvement..
- Disc height at each annual timepointcompared to baseline (6 weeks) in the IDE study for the Simplify Disc and for the historical control ACDF, as measured by standard lateral radiograph (spot film, distance of 6 feet, centered at C5 with patient upright).
- Adjacent level deterioration at each annual timepoint compared to baseline in the IDE study for the Simplify Disc and for the historical control ACDF.
- Displacement or migration of the device; only changes of > 3 mm will be considered significant due to the margin of error in radiographic determination of displacement distances.
- Treatment satisfaction at at each annual timepoint for the SimplifyDisc and \*for the historical control ACDF.
- Health Survey (SF-12v2) for the Simplify Disc at each annual timepoint compared to baseline in the IDE study.
- Dysphagia Handicap Index (DHI scale) for the Simplify Disc at each annual timepoint compared to baseline in the IDE study.

1 Hacker *et al., supra* note 7.

0				
			l	
•				
•				
•				
2.3.7.10		l		
	-			

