#### 2.3.7.5 SAMPLE SIZE ANALYSIS

For the purposes of sample size calculation, it is estimated that 85% of the estimated 142 Simplify Disc subjects (N=121) who are not terminal failures or lost to follow-up by Month 24 will be available at year 5. It is estimated that 60% of the estimated 106 (N=64) Control subjects who are not terminal failures or lost to follow-up by Month 24 will be available at year 5.

Based on these results, it was conservatively estimated that the 5-year overall success rates would be 70% of the observed rates, that is, 65% and 50% for Simplify Disc and historical ACDF control, respectively. If the success rates in both groups are larger, statistical power will be larger and so this power analysis would be conservative. With sample sizes of 121 and 64, and assuming 65% and 50% success, the power to detect non-inferiority is 96% at a one-sided 0.05 significance level.

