#### **2.3.7.8** ANALYSIS OF SECONDARY ENDPOINTS AND ADVERSE EVENTS

Secondary effectiveness endpoints will be compared between groups over time using group differences and 95% confidence intervals for group differences. Adverse events will be summarized by event counts and per subject incidence rates for categories of AE, for specific AEs, by relationship to device and procedure, and for SAEs. Counts will also be summarized by time of onset category and by AE severity. Where applicable, AE summary tables will include 95% confidence intervals for group differences in incidence rates.

For each study group and for important subgroups separately, the primary outcome (i.e., patient success) and secondary endpoints, as well as the incidence of specific complications, will be tabulated and presented by follow-up interval. Comprehensive tables will provide frequency and percentage distributions and descriptive statistics as appropriate in total and for each study group separately. Tables and graphical displays will be provided for both the primary effectiveness and safety populations as appropriate.

Survival analysis methods will be used to describe time to event outcomes including time to secondary surgical intervention.

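### The only two-arm pain scale is reported as patient counts around a 20 mm change, and no between-group mean VAS difference is prespecified; this costs precision on a secondary endpoint.

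*Combined protocol and SAP*

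**What the plan says.** Section 2.3.7.8.1 (Secondary Endpoints) frames the endpoint as "Clinically significant improvement in one or more radicular symptoms or myelopathy at each annual timepoint compared to baseline". The VAS is one graded element of it, beside motor and sensory status. The data are to show the "number of patients who improved (numbers will be stratified to reflect clinical improvement), who remain unchanged, and who deteriorated" at each study time point. For the VAS, the dividing line is: "Changes of at least 20 mm on a 100 mm scale will be regarded as clinically significant". Four pain locations are listed. Combined neck-and-arm pain is the one kept for comparison with ACDF; neck, left arm and right arm are collected for Simplify Disc only.

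On analysis, section 2.3.7.8 says: "Secondary effectiveness endpoints will be compared between groups over time using group differences and 95% confidence intervals for group differences". It adds: "Comprehensive tables will provide frequency and percentage distributions and descriptive statistics as appropriate". Neither section attaches a hypothesis test, an alpha level or a power figure to the VAS. Neither gives cut-points for the strata within the improved group, an ordinal method for them, a difference in mean VAS, or adjustment for baseline VAS.

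**The concern.** The VAS is a 0–100 mm measurement taken at baseline and at every annual visit. If the comparison with ACDF uses only the 20 mm line, a fall of 19 mm and a fall of 20 mm land in different categories, and how far a patient moves beyond the line is lost. When most patients in both arms improve by more than 20 mm, the two percentages crowd towards 100% and separate poorly.

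Only about 121 Simplify and 64 ACDF subjects are expected at year 5 (section 2.3.7.5), so secondary intervals will be wide in any case. A real pain difference, in either direction, is then more likely to come with an interval that covers zero. The control is also historical and non-randomised (section 2.3.3), so choosing a scale and a model after the data are seen would be hard to defend.

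**Working it through.** **1. The plan's own power figure.** It concerns CCS only: 121 and 64 subjects, 65% and 50% success, margin 0.10, one-sided 0.05 (sections 2.3.7.2 and 2.3.7.5).

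SE = √(0.65·0.35/121 + 0.50·0.50/64) = 0.0761. Power = Φ(0.25/0.0761 − 1.645) = 95.0%; the Farrington–Manning form gives 95.3%. The stated 96% is reproduced to about one point. There is no VAS figure to reproduce.

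The same inputs give a yardstick for the cost of one cut. Power to show a difference in proportions is Φ(0.15/0.0761 − 1.645) = 62.8%. If those proportions came from cutting a normal scale, the shift would be 0.385 SD with SE √(1/121 + 1/64) = 0.1546, and power Φ(0.385/0.1546 − 1.645) = 80.2%. The gap is 17 points.

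**2. One 20 mm cut against a comparison of means.** Assumptions: normal VAS change, common SD, pure shift, two-sided 0.05 to match a 95% CI. A shift that the mean comparison detects with power P is d = (1.960 + z_P)·0.1546. For P = 80%, d = (1.960 + 0.842)·0.1546 = 0.433 SD, or 13.0 mm at an assumed SD of 30 mm. With ACDF responder rate q, the Simplify rate is p = Φ(z_q + d). Responder power is Φ((p − q − 1.96·SE₀)/SE₁), with SE₀ pooled and SE₁ unpooled.

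Example, q = 70%: p = Φ(0.524 + 0.433) = 83.1%, SE₀ = 0.0634, SE₁ = 0.0667, power = Φ((0.1308 − 0.1243)/0.0667) = 53.9%, a loss of 26 points.

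Loss in percentage points:

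| ACDF responder rate | Mean power 50% | 80% | 90% | 95% |
|---|---|---|---|---|
| 40% | 16.0 | 19.7 | 16.9 | 13.2 |
| 50% | 15.5 | 19.7 | 17.4 | 14.0 |
| 70% | 18.6 | 26.1 | 25.0 | 21.9 |
| 80% | 22.5 | 33.4 | 33.6 | 31.1 |
| 85% | 25.3 | 38.7 | 39.9 | 38.1 |

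The range is about 13 to 40 points. An unpooled Wald interval does somewhat worse at high rates: at q = 70%, Φ(0.1308/0.0667 − 1.96) is about 50% instead of 53.9%.

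Precision relative to the effect: on the mm scale effect/SE = 0.433/0.1546 = 2.80. At q = 50% the responder scale gives 0.1675/0.0758 = 2.21, so its interval is 2.80/2.21 = 1.27 times as wide relative to the effect. At q of 70–84% the ratio is about 1.4 to 1.75.

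**3. Ordered categories.** Mann–Whitney comparison, 3,000 simulated trials, SD 30 mm, mean-comparison power set at 80%:

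| ACDF mean fall | 2 levels | 3 levels | 5 levels (cuts −20, 20, 40, 60) |
|---|---|---|---|
| 20 mm | 60.6% | 65.0% | 73.8% |
| 30 mm | 56.9% | 58.5% | 73.4% |
| 40 mm | 50.8% | 50.4% | 71.2% |

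Three levels recover little or nothing. Five levels leave a loss of about 6 to 9 points. The five-level cuts are assumed; the plan gives none.

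**4. A bounded VAS, separating the cut from baseline adjustment.** Assumptions: baseline mean 70 mm, SD 15; follow-up SD 25 or 30; scores held to 0–100; ACDF fall 30, 40 or 50 mm; 10 mm extra fall with Simplify; baseline correlation 0.2 or 0.4. Twelve scenarios, 4,000 trials each. The chance that a 95% CI excludes zero in favour of Simplify:

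| Analysis | Range |
|---|---|
| Single 20 mm cut | 22–52% |
| Three levels, scored | 21–51% |
| Five levels, scored | 41–71% |
| Mean change, unadjusted | 44–76% |
| ANCOVA on baseline, robust SE | 52–78% |

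Example (fall 40, SD 25, correlation 0.2): 36% for the cut, 60% for five levels, 64% for mean change, 72% for ANCOVA. Of the 36-point gap between the first and last, about 28 come from the cut and 9 from baseline adjustment (rounded). Across scenarios, five scored levels lose about 3 to 5 points against unadjusted mean change. Baseline adjustment adds about 1 to 12; the low end cannot be told from zero given simulation error.

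**The case against.** **No test exists whose power could fall.** This stands. Study success and the superiority claim rest on CCS (sections 2.3.7.2 and 2.3.7.6). The percentages above describe whether an interval would exclude zero, not the power of a planned test.

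**The plan does not describe one binary cut.** This stands in part. It has three categories, and the improved group is to be stratified, so a reader who infers that falls of 20 mm and 80 mm must count alike goes beyond the text. Yet the strata have no boundaries and no ordinal analysis is named, so the recovery seen with five levels is not something the plan secures.

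**A mean comparison is not excluded.** True. Group differences with CIs can cover continuous measures, and 20 mm can be read as a threshold for interpretation. The text after the secondary endpoint list is also broken in the available copy, so the claim is limited to what can be read. There the mean comparison is unspecified, and the general line on descriptive statistics promises tables by group, not an adjusted difference with a CI.

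**The size depends on assumed VAS values.** This stands; hence the ranges.

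**A mean model needs a rule that a responder count does not.** This stands. Section 2.3.6.2.3 takes Simplify subjects out of the study after the visit following index-level surgery. A count could class them as not improved; a Month 60 mean needs a stated assumption. The fix must supply it.

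**Conclusion.** The point holds as a loss of precision on a secondary endpoint. At 121 and 64 subjects, a single 20 mm cut lowers the chance that a 95% CI excludes zero by about 13 to 40 points against a comparison of means. That range assumes ACDF responder rates of 40–85% and mean-comparison power of 50–95%; the loss is larger when responder rates are higher still. Five ordered levels would reduce it to about 3 to 9 points. Baseline adjustment is a separate gain of about 1 to 12 points and should not be charged to the cut.

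Three stronger readings are tempting and not supported. A loss of at least 20 points is not general: part of the assumed range gives 13 to 17. The interval is not wider in absolute terms, because percentage points and millimetres are different scales; it is wider only relative to the effect. And nothing here threatens the primary result or shows that the sponsor has ruled out analysing mean VAS.

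**What to change.** In section 2.3.7.8.1, keep the 20 mm table of improved, unchanged and deteriorated patients as the clinical description, and define the strata within the improved group.

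Add, as the prespecified between-group pain comparison at Months 36, 48 and 60, the difference in mean neck-and-arm VAS in mm with its 95% CI. Estimate it from a linear or mixed model with device group, baseline VAS and the existing PS subclass, using robust standard errors.

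State, identically for both arms, how subjects with index-level surgery or missing VAS enter the model: for example, one named primary version and one sensitivity analysis under a different assumption.

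The cost is SAP wording and one further model on data already collected in both arms. The downside is one more secondary estimate to report and an explicit missing-data assumption to defend. The CCS definition and primary test stay as they are.

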#### 2.3.7.11 OTHER OUTCOMES

Range of motion in flexion/extension at the operative level. Cobb angle measurements of the functional spinal unit will be made. Differences in range of motion of at least 2 degrees when compared to baseline in the IDE study will be considered clinically significant. Assessments will include comparison of range of motion at 60 months to baseline in the IDE study for the Simplify Disc and for the historical control ACDF and to normal range of motion at the operative level, based on White and Panjabi. Evaluation of these criteria will be based on anterior/posterior, lateral, and flexion/extension X-rays.

Radiographs will be used to monitor the occurrence of some of the above adverse events, including subsidence of the device into the adjacent disc or other changes in the implant, and spinal instability. In addition, at each visit, after the subject has had an opportunity to spontaneously mention any

 White and Panjabi: Clinical Biomechanics of the Spine. 2nd ed. Philadelphia, JB Lippincott Co.,1990.

problems, the investigator will elicit information concerning adverse events by asking standard questions. Adverse events considered unusual for the patient population (i.e., occurring with greater frequency than anticipated or with greater severity than anticipated), key to safety or efficacy, or device related will require detailed reporting on the appropriate case report form.

# 2.3.8 SAFETY ASSESSMENT

#### 2.3.8.1 Adverse Events

An adverse event is defined as any clinically significant undesirable clinical occurrence in a subject. Adverse events, whether or not device related, must be reported on the appropriate case report form. Adverse events will be classified based on seriousness, relationship to device and procedure, and severity by the study investigator. Any adverse event that occurred prior to treatment with the medical device will be documented in the patient's pre-operative medical history in the Simplify Disc study. Only adverse events which occurred in the Month 36 through Month 60 visits or are continuing from Simplify Disc IDE study or are new or have worsened during the course of this study will be evaluated in the safety assessment.

Analysis of adverse events will be conducted using the methods specified in section 2.3.7.8.

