#### 2.2 PURPOSE OF STUDY

This study is intended to demonstrate the 5-year long-term safety and efficacy of the Simplify® Cervical Artificial Disc ("Simplify Disc") in subjects enrolled in the non-randomized Simplify Disc IDE study. This study was conducted under IDE G140154.

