# 2.3 PROTOCOL STUDY CONDUCT

## 2.3.1 STUDY OBJECTIVE

The objective of this clinical study is to evaluate the 5 year long-term safety and effectiveness of the Simplify Disc compared to conventional anterior cervical discectomy and fusion ("ACDF") for treatment of intractable radiculopathy (arm pain and/or a neurological deficit) with or without neck pain or myelopathy due to a single-level abnormality localized to the level of the disc space at one level from C3 to C7 that is unresponsive to conservative management.

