# 2.3.5 STUDY DESIGN

### 2.3.5.1 OVERALL STUDY DESIGN

This is a prospective, multi-center post-approval study to evaluate the 5-year long term safety and effectiveness of the Simplify Disc. The historical control population will only include the fusion subjects who were selected using a PS model developed in the Simplify Disc IDE study and approved PMA. The Simplify Disc data from the training subjects will be summarized separately and not used in the primary comparison to control. Study subjects will be evaluated annually ( $\pm$  2 months) for components of the primary endpoint, secondary study endpoints and safety up through 5-year post-implantation. Primary study success will be evaluated at the 5-year timepoint.

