## 2.3.6.2 STUDY EVALUATIONS, PROCEDURES AND ASSESSMENTS

Follow-up evaluations annually at Month 36, Month 48, and Month 60 will include:

- AP and lateral X-rays (plain films);
- Flexion-extension X-rays (used to determine range of motion);
- Lateral bending films (Simplify Disc only);
- Radiographic core lab evaluations;
- Dysphagia Handicap Index (Simplify Disc only);
- NDI assessment;
- SF-12v2 Health Survey (Simplify Disc only);
- VAS pain assessments (neck and arm; neck, left arm and right arm (Simplify Disc only));
- Neurologic evaluation;
- Study related medication status (Simplify Disc Only);
- Work status;
- Treatment satisfaction assessment and
- Adverse events as defined by Section 2.3.8 of this protocol.
- •

Neurologic status will be evaluated by a qualified evaluator, who may be an MD, DO, an RN or a PA. The neurologic evaluation will include a motor and sensory assessment, reflex responses and the determination of the presence or absence of dysphagia, dysphonia, clumsiness, foot drop, atrophy, cramping, muscle spasms, numbness and gait abnormality.

Muscle strength will be graded for the deltoid (C5), biceps (C6), and triceps (C7) according to a 6point scale where 0 = no movement, 1 = trace of muscle contraction; 2 = active movement without gravity; 3 = active movement against gravity; 4 = active movement against gravity/resistance; and 5 =normal response.

Study related medication status will include only medications taken or administered for the following

- Pain (any type);
- Inflammation (any type);

- Muscle relaxation;
- Numbness &/or tingling;
- Hormonal replacement therapy and
- Other medications related to or given for the subject's spinal condition.

All radiographic endpoints will be evaluated independently by one core laboratory.

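### The adverse-event rule leaves out events that began and resolved during the IDE and gives no carry-over rule for the ACDF controls, so the safety tables are not the stated 5-year comparison

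*Combined protocol and SAP*

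**What the plan says.** Three sections set a 5-year safety aim. Section 2.2 says the study is "intended to demonstrate the 5-year long-term safety and efficacy". Section 2.3.1 makes the aim comparative: "evaluate the 5 year long-term safety and effectiveness of the Simplify Disc compared to conventional anterior cervical discectomy and fusion". Section 2.3.5.1 has subjects evaluated each year for components of the primary endpoint, "secondary study endpoints and safety up through 5-year post-implantation".

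Section 2.3.8.1 then defines which adverse events enter the safety assessment: "Only adverse events which occurred in the Month 36 through Month 60 visits or are continuing from Simplify Disc IDE study". The same sentence adds one further route, for events that start or get worse while the PAS is under way. It sends the analysis to section 2.3.7.8, which plans counts, per-subject incidence and tabulation by onset category, and adds: "Where applicable, AE summary tables will include 95% confidence intervals for group differences in incidence rates".

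The PAS visits are set in section 2.3.6.2: "Follow-up evaluations annually at Month 36, Month 48, and Month 60 will include". Section 2.3.3 states that the ACDF controls come from a separate, non-concurrent historical study.

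**The concern.** The rule opens with a word of exclusion, so any event that meets none of its routes is left out. If a class of events from the first years after surgery is removed, the tables describe late follow-up, although the objective promises a 5-year comparison. A reader who takes the printed incidences as 5-year risks would understate them.

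The second issue is comparability. A group difference in incidence means something only if both groups are counted over the same window by the same rule. The carry-over route refers to the study in which the Simplify subjects were treated. Section 2.3.8.1 gives no corresponding statement for the study that supplied the controls.

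**Working it through.** **Inputs.** The routes come from section 2.3.8.1, the visit months from section 2.3.6.2, and the expected year-5 numbers from section 2.3.7.5. Those numbers reproduce: 0.85 × 142 = 120.7, stated as 121, and 0.60 × 106 = 63.6, stated as 64. The plan states no adverse-event rate and no precision for the safety comparison, so there is no plan figure to reproduce for the point itself. An IDE end at Month 24 is inferred from the Month 24 results in sections 2.3.7.4 and 2.3.7.5. It is an assumption.

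**Step 1: test each class of event against the rule.**

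| Event | In Month 36-60 visits? | Continuing from the IDE? | New or worsened in this study? | Counted? |
|---|---|---|---|---|
| Began and resolved during the IDE | No | No | No | No, on any reading |
| Began during the IDE, still present (Simplify) | – | Yes | – | Yes |
| Began in the historical study, still present (ACDF) | Depends on reading | Not named | Depends on reading | Not specified |
| Began after the last IDE visit, resolved before Month 36 | Depends on reading | No | Depends on reading | Ambiguous |
| Onset Month 36-60 | Yes | – | Yes | Yes |

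**Step 2: coverage of new onsets.** If the rule reaches back to Month 24, it covers 36 of 60 months (60%). If it starts at Month 36, it covers 24 of 60 months (40%).

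**Step 3: what a shorter window does to incidence (illustration).** With an assumed 5-year incidence I, constant hazard and no carry-over, the incidence over k months is 1 − (1 − I)^(k/60). For I = 40%: 1 − 0.60^(36/60) = 26.4% and 1 − 0.60^(24/60) = 18.5%.

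| Assumed 5-year incidence | Months 24-60 | Months 36-60 |
|---|---|---|
| 20% | 12.5% | 8.5% |
| 40% | 26.4% | 18.5% |
| 60% | 42.3% | 30.7% |

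Clustering of events soon after surgery would make the shortfall larger. Carry-over events, which the rule does admit, would make it smaller.

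**Step 4: what one-sided carry-over would do, if applied literally (illustration).** Suppose both groups have the same new-event incidence r, and a fraction c of Simplify subjects independently have a continuing event. The Simplify incidence is then 1 − (1 − r)(1 − c), and the spurious difference is c(1 − r).

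| r | c = 5% | c = 10% | c = 20% |
|---|---|---|---|
| 20% | +4 points | +8 points | +16 points |
| 40% | +3 points | +6 points | +12 points |

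With 121 and 64 subjects, the standard error of the difference is 6.3 to 7.6 points across these cases. For r = 20% and c = 10% it is √(0.28 × 0.72/121 + 0.20 × 0.80/64) = 6.5 points. A 10% one-sided carry-over would therefore be about as large as the standard error, and it would run against Simplify.

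**The case against.** The strongest reply is that this is a follow-up of subjects whose IDE results already supported an approved PMA, so restricting the new report to later events may be a deliberate choice. The 5-year phrase in section 2.3.5.1 can be read as how long evaluation continues, not as a promise of cumulative tables. Cumulative safety is also partly covered. Device failure and index-level surgery count by Month 60 in the primary endpoint (section 2.3.7.1), and time to secondary surgery is analysed by survival methods (section 2.3.7.8). This part stands: the problem concerns the other adverse events. It does not remove the conflict, because section 2.3.1 states a 5-year comparison with ACDF and nothing labels the tables as late-period only.

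A reader might go further and infer three things that the documents do not support.

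- *Events between the end of the IDE and PAS entry are lost.* Section 2.3.7.11 has investigators elicit adverse events at each visit, so an event in that interval may count when it is reported at Month 36. The timing of PAS consent is not given, and no section says when the study starts for a subject. The text is ambiguous and does not establish a loss.
- *The controls are deliberately counted under a different rule.* Sections 2.3.2, 2.3.7.1 and 2.3.7.8.1 use the IDE study loosely as the baseline reference for both groups. What is shown is an unwritten control rule. The asymmetry follows only from a literal reading.
- *Lost events would favour Simplify.* That would need control events from the same months to be counted, and no section gives the controls a wider window.

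**Conclusion.** The point holds in a limited form. On any reading, events that began and resolved during the IDE are outside the safety assessment, so the adverse-event tables do not give the 5-year comparison with ACDF in the objective. The carry-over rule for the controls is not written, although between-group confidence intervals are planned. A literal application would bias the difference against Simplify. The handling of events before Month 36 is unclear, and the net direction is unknown.

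The size cannot be derived from the plan, because it gives no adverse-event rates. The figures above rest on assumed incidences, a constant hazard and assumed carry-over fractions, and show only what kind of distortion is possible. The primary test is unaffected. This is a correction to secondary safety reporting that is worth making, and it does not threaten the study's main conclusion.

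**What to change.** Replace the limiting sentence in section 2.3.8.1 with one onset window and one carry-over rule. Express both in months since index surgery, apply them identically to Simplify and to the ACDF source study, and name that study. State that the first PAS visit records events since the last IDE visit and that these are counted.

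In section 2.3.7.8, add a cumulative Month 0-60 table for the PS-selected subjects of both groups, with subtables for Months 0-24 and after Month 24. Label any later-period table with its true window.

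Crude percentages will not do for the cumulative table. Expected year-5 availability is 85% against 60%. The PS-selected sample of 150 and 117 also exceeds the estimated 142 and 106 by 150 − 142 = 8 Simplify and 117 − 106 = 11 control subjects. Use person-time rates or time-to-first-event estimates censored at last contact, and say how events are counted in subjects who never enter the PAS, including those excluded for index-level surgery during the IDE. Censoring needs a caveat, because section 2.3.6.2.3 discontinues subjects after secondary index surgery.

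The cost is protocol and SAP wording, a merge of IDE and historical adverse-event data, and larger reported incidences. That the historical data are available in this detail is an assumption. If they are not, the fallback is to state the restricted window openly and not present the tables as 5-year safety.
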